## **5. appraise**

### **5.1 Primary and secondary endpoints / outcome evaluation**

Main end point

- The ORR was based on the RECIST 1.1 assessment.
- The PFS based on the RECIST 1.1 assessment.

Secondary end point

- According to the RECIST vi. The DoR, DCR, TTR, TTP, and OS as assessed by I.
- PK characteristics: including serum concentrations of cadadilimumab at different time points after cadilimumab administration.
- Immunogenicity assessment: Number and percentage of subjects presenting with detectable antimicrobial antibodies (ADA).
- To assess the correlation of PD-L1 expression with efficacy in tumor samples by immunohistochemical detection.
- To evaluate the association of EB virus (EBV) DNA copy number in blood and antitumor activity of caadilimumab in subjects with advanced NPC.

Health-related Quality of Life Assessment HRQoL-as measured using the European Organization for Research and Treatment of Cancer Quality of Life Questionnaire-Core 30 (EORTCQLQ-C30) and EORTCQLQ-H & N35.

## **5.2 Safety evaluation (necessary)**

Safety:, incidence and severity of adverse events (AEs), clinically significant abnormal laboratory findings.

## **6. Adverse events and serious adverse events (must)**

All treated patient (APaT) population was used for the safety data analysis for this study. All treated patient populations included all patients receiving at least 1 dose of study medication.

### **6.1 Adverse events**

Definition: Any adverse medical event between the entry of the patient and the last follow-up, whether causally related to the trial drug.

Adverse events were truthfully recorded during the trial, including the time, severity, duration, measures taken and outcome of the adverse events.

The severity criteria for adverse events: according to the WHO evaluation criteria for adverse drug reactions (Annex 4). The adverse reactions listed in the table are indicated in the following case:

- Mild: it does not affect the normal function of the subject.
- Moderate: to affect the normal function of the subjects to some extent.
- Severe severity: obviously affecting the normal function of the subjects.

### **Criteria for determining the relationship between adverse events and trial drug:**

The Investigator should assess the possible association between the adverse event and the trial drug according to the following criteria:

Positive concern: the timing of the reaction, the timing of the known type of response of the test drug, improvement after withdrawal, and repeated administration reappeared.

Related to: the timing of the reaction, the known type of response to the trial drug, and the patient's clinical status or other treatments.

Probably unrelated: the timing of the reaction does not match the chronological order of the medication, the response is not quite within the known

type of response given by the trial drug, or because of the patient's clinical status or other treatments.

No: The time of the response does not conform to the chronological order of the medication, the response has the response type known to the non-trial drug, the patient's clinical status or other treatment methods may also produce the response, the improvement of the disease state or the elimination of other treatment methods, and the reuse of other treatment methods.

It cannot be determined that there is no clear relationship between the time of the reaction and the chronological order of the medication, the response is similar to the known type of response of the test drug, and other drugs used may also cause the same response.

## 6.2 Serious Adverse Events

### 6.2.1 Determination of serious adverse events

- die
- Life is in danger
- Leading to a prolonged hospitalization or hospital stay
- Permanent or severely disabling condition
- Lead to congenital malformations, defects

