### 6.2.2 Any serious adverse reaction occurring during the clinical trial or within 30 days of the last treatment, whether it is related to the drug, should be immediately and orally reported to the study director, the Ethics Committee and the sponsor within 24 hours.

### 6.2.3 The investigator should follow up for serious adverse reactions until the symptoms disappear or the condition is stable.

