**Table 2: The recommended principles for dose adjustment and toxicity management of AK 104 immune-related AEs**

Immune-related AEs	Toxicity level	Measures taken against AK 104	Management of irAE (corticosteroids and other treatments)	Monitoring and follow-up

pneumonia	Level 2	Suspension of medication	Corticosteroid hormone (initial dose of 1-2mg / kg prednisone or equivalent), then tapered thereafter	The subject was monitored for the symptoms and signs of pneumonia. Subjects with suspected pneumonia by imaging evaluation and were started on corticosteroid hormone therapy. Prophylactic use of antibiotics to prevent opportunistic infections
	Grade 3 – 4, or recurrent grade 2	Permanent withdrawal of drugs		
Diarrhea / enteritis	Level 2-3	Suspension of medication	Corticosteroid hormone (initial dose of 1-2mg / kg prednisone or equivalent), then tapered thereafter	Participants were monitored for symptoms and signs of gastroenteritis (diarrhea, abdominal pain, hematology, blood, stool, with or without fever) or bowel perforation (peritoneal irritation or intestinal obstruction). Subjects with grade 2 diarrhea and suspected enteritis should consider consulting a gastroenterologist for endoscopy to exclude enteritis
	Level 4	Permanent withdrawal of drugs		
AST/ALT	Level 2	Suspension of	Corticosteroid (initial	Monitor liver

Elevated or with an elevated bilirubin		medication	dose 0.5-1mg / kg prednisone or equivalent), tapered	function (weekly or more frequently until liver enzymes return to baseline or remain stable)
	Level 3	Suspend or permanently	Corticosteroid hormone (initial dose of 1-2mg / kg prednisone or equivalent), then tapered thereafter	
	Level 4	Permanent withdrawal of drugs	Corticosteroid hormone (initial dose of 1-2mg / kg prednisone or equivalent), then tapered thereafter	
Type 1 diabetes mellitus (T1DM) or hyperglycemia	New T1DM or hyperglycemia (related to cell failure)	Suspension of medication	T1DM subjects were started on insulin replacement therapy and hyperglycemic subjects were started on antidiabetic agents	The subject was monitored for blood glucose, or other symptoms and signs of diabetes
hypophysitis	Level 2	Suspension of medication	Use of corticosteroid hormones and, if clinically indicated, initiate hormone replacement therapy	Monitor for symptoms and signs of hypophysitis (including pituitary and adrenal dysfunction)
	Level 3-4	Suspend or permanently		

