hyperthyreia	Level 2	cont.rem	Treatment with nonselective receptor blockers (e. g. propranolol) or thioamide (if appropriate)	Monitor for the symptoms and signs of thyroid disease
	Level 3-4	Suspend or permanently		
hypothyreia	Level 2-4	cont.rem	Thyroid hormone replacement therapy was initiated based on standard therapy (e. g. L Thyroxine or triiodothyronine)	Monitor for the symptoms and signs of thyroid disease

Nephritis and renal insufficiency	Level 2	Suspension of medication	Corticosteroid hormone (initial dose of 1-2mg / kg prednisone or equivalent), then tapered thereafter	Monitor for changes in renal function
	Level 3-4	Permanent withdrawal of drugs		
carditis	Level 1	Suspension of medication	Corticosteroid hormones were used based on the type and severity of the AE	Ensure adequate evaluation to confirm the cause and or to exclude other causes
	Level 2	Suspend or permanently		
	Level 3-4	Permanent withdrawal of drugs		
All of the other irAEs	Level 2, that could not be tolerated or persisted	Suspension of medication	Corticosteroid hormones were used based on the type and severity of the AE	Ensure adequate evaluation to confirm the cause and or to exclude other causes
	Level 3	AEs based on type of AE suspension or permanent withdrawal include but are not limited to Guillain-Barre syndrome, encephalitis, etc		
	Grade 4 or recurrent grade 3	Permanent withdrawal of drugs		
1. Suspension or permanent withdrawal will be decided after discussion between the investigator and the medical supervisor pay attention to:				

When the AE returns to grade 0-1 or baseline, corticosteroid hormones began to be gradually reduced for more than 4 weeks;

For AK 104 suspension: restart AK 104 if the AE returns to Grade 0-1 or baseline with corticosteroid tapering (10mg prednisone or equivalent dose) and if the AE does not resolve within 12 weeks after the last dose or 12 weeks;

For severe and life-threatening irAEs, intravenous corticosteroids and sequential oral hormone therapy should be started, and if corticosteroids are not effective, other immunosuppressants should be considered;

For subjects with grade 3-4 immune-related endocrine disorders requiring AK 104 suspension, allow medication to resume when the AE returns to level 2 and is controlled by hormone replacement therapy or achieves metabolic stability (e. g., T1DM).

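### The SAE definition in section 6.2.1 has no criterion for other medically important events, so some immune toxicities that end AK 104 under Table 2 can miss 24-hour reporting and the SAE count

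*Protocol*

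**What the plan says.** Protocol section 6.2.1 gives the SAE criteria as a bare list. After death come "Life is in danger", "Leading to a prolonged hospitalization or hospital stay", "Permanent or severely disabling condition" and "Lead to congenital malformations, defects". Section 6.2.2 follows directly. The list has no sixth item and no wording that makes it open-ended.

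Section 6.2.2 covers "Any serious adverse reaction occurring during the clinical trial or within 30 days of the last treatment", related to the drug or not, and says that it "should be immediately and orally reported to the study director, the Ethics Committee and the sponsor within 24 hours". No other event class has a reporting deadline to those bodies.

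Table 2 (section 8.4) sets the action on AK 104 by grade. For pneumonia, the row "Grade 3 – 4, or recurrent grade 2" leads to permanent withdrawal. So do grades 3 and 4 in the row "Nephritis and renal insufficiency", and grades 3 and 4 of carditis.

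The safety part of the scenario summary plans separate summaries of all AEs, drug-related AEs, SAEs, and AEs and AESIs leading to discontinuation.

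**The concern.** Seriousness under 6.2.1 depends on outcome, and in practice often on whether the subject was admitted. Withdrawal under Table 2 depends on grade. The two rules need not agree, and nothing in the protocol bridges the gap. An immune toxicity that the protocol treats as grave enough to end AK 104 for good can be managed without admission, without danger to life and without lasting disability. Followed as written, it is then not serious.

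Two things are at stake. One is prompt notice to the ethics committee and sponsor of immune toxicity from a PD-1/CTLA-4 agent given with chemotherapy. The other is the SAE row of the safety summary, which would partly reflect admission practice rather than medical importance.

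**Working it through.** **Rule comparison.** Each Table 2 entry is set against the five criteria of 6.2.1. Table 2 is used only to show the mismatch; no view is taken on its clinical rules.

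- Pneumonia, recurrent grade 2: permanent withdrawal. None of the five criteria need be met. This is the clearest case.
- Nephritis grade 3 and carditis grade 3: permanent withdrawal. Serious only if the subject is admitted or a stay is prolonged, or if the event is life-threatening, disabling or fatal. Many will be admitted; those that are not fall outside the list.
- Other immune-related AEs, recurrent grade 3: permanent withdrawal. The same reasoning applies.
- Grade 4 events, including AST/ALT: permanent withdrawal in several rows, but most would meet the danger-to-life criterion. These add little to the point.
- Carditis grade 2 and AST/ALT grade 3: suspension or permanent withdrawal, so withdrawal is optional. These are weak examples.

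**Search for a backstop.** AESI appears in the acronym table and in the scenario summary's list of tabulations, with no list of events and no deadline. GCP and regulatory requirements are mentioned in section 9.1, but that section concerns consent and does not amend 6.2.1. No other section widens the definition.

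**Size.** The protocol gives no figure for events that end treatment without being serious, so the size has to be approximated.

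- From section 1.1.2: treatment-related AEs causing study withdrawal in 6.6% of 228 subjects on AK 104 alone.
- From section 3.2: 30 subjects planned.
- Assumption, not in the protocol: 25% to 75% of such events meet none of the five criteria.

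Expected withdrawals: 30 × 0.066 = 1.98.

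Expected number that escape: 1.98 × 0.25 = 0.5 to 1.98 × 0.75 = 1.5.

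Per-subject probability of one that escapes: 0.066 × 0.25 = 0.0165 to 0.066 × 0.75 = 0.0495.

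Chance of at least one in 30, treating subjects as independent: 1 − (1 − 0.0165)^30 = 0.39 to 1 − (1 − 0.0495)^30 = 0.78.

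**The case against.** The strongest reply is that almost nothing is lost. Section 6.1 has every AE recorded with its severity, duration, measures taken and outcome. The primary safety endpoint in section 2.2.1 is the incidence and severity of all AEs, not of SAEs. The scenario summary tabulates AEs leading to discontinuation in their own right. This stands. A reader might infer that the primary endpoint under-counts immune toxicity; it does not, because these events are counted and graded there whether or not they are serious.

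A reader might also infer that the safety lead-in is compromised. Section 3.1 does not support that. The lead-in rests on the investigator's own safety assessment, and the later check on whether 6 of 15 subjects do not tolerate treatment. Neither is triggered by an SAE count.

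Table 2's footnote requires discussion with the medical supervisor where the choice is between suspension and permanent withdrawal. That helps for those rows, but it has no deadline, does not reach the ethics committee, and is not stated for rows where permanent withdrawal is the only action.

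On size, 1 − (1 − 0.066)^30 = 0.87 is tempting to quote. It is the chance of at least one treatment-related withdrawal of any kind, not of one that escapes SAE status. Section 1.1.2 also reports drug-related SAEs in 11% of the same 228 subjects, above the 6.6% withdrawal rate. Most of those withdrawals could already have been serious, so the escaping share could lie below 25%. The documents do not give the overlap.

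**Conclusion.** The omission is real and rests on the protocol's own text: a closed list of five criteria, a 24-hour route tied to that list, and withdrawal rules tied to grade. Some immune toxicities that end AK 104 can therefore miss expedited reporting and the SAE row. Recurrent grade 2 pneumonia is the clear case; grade 3 nephritis or carditis without admission are further ones. The loss goes no further than those two outputs.

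About 0.5 to 1.5 of 30 subjects would be affected, with a 39% to 78% chance of at least one. This depends on the assumed 25% to 75% share and on a monotherapy rate at mixed doses carried over to AK 104 plus platinum, for which the protocol gives no rate. The gap itself does not depend on these figures. It should be closed because patient-safety reporting is involved and the change is small.

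A reader might conclude that every discontinuation for toxicity ought to be an SAE. The documents do not support that, because it equates the action taken with seriousness. Sections 8.2 and 8.4 allow AK 104 to be ended for several low-grade AEs together, and Table 1 withdraws subjects after a second grade 2 infusion reaction. Classing all of these as serious would inflate the SAE rate and duplicate the discontinuation summary.

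**What to change.** Add a sixth criterion to section 6.2.1: any other event that the investigator judges medically important. State beside it that each toxicity for which Table 2 calls for permanent withdrawal of AK 104 must be assessed against this criterion and the judgment recorded, without being classed as serious automatically. The 24-hour rule in 6.2.2 and the SAE summary then apply to events so judged, with no other change to either.

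The cost is one bullet and one sentence, at most a few extra expedited reports over the trial, and a slightly less favourable SAE rate. Table 2 and the treatment rules are untouched.

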### 6.2.2 Any serious adverse reaction occurring during the clinical trial or within 30 days of the last treatment, whether it is related to the drug, should be immediately and orally reported to the study director, the Ethics Committee and the sponsor within 24 hours.

### 6.2.3 The investigator should follow up for serious adverse reactions until the symptoms disappear or the condition is stable.

## **7. Statistical analysis and statistical methods (necessary)**

### **7.1, and the analysis set**

#### **7.1.1, and the enrollment analysis set**

The enrollment analysis set included all subjects who signed the ICF into the study.

#### **7.1.2 Full Analysis set**

The full Analysis set (FAS) included all subjects who had received at least one dose of study drug and had measurable lesions at baseline (as defined by RECIST v1.1).

#### **7.1.3 Safety Analysis Set**

The Safety Analysis Set (SS) includes all subjects who have received at least one study medication. Analysis was performed based on the treatment that the subject actually received.

#### **7.1.4 Pharmacokinetic analysis set**

Pharmacoanalysis Set (PKS): Subjects who had received at least 1 study drug and had at least 1 effective postdose plasma concentration data.

#### **7.1.5 Immunogenicity analysis set**

The immunogenicity analysis set included all subjects who were randomized and used at least one study drug, pre-medication and at least one post-medication immunogenicity assessment data.

## **8. Medical treatment and protection of the subjects (necessary)**

### **8.1 Assessment of risk in the study and risk management measures and plan (necessary)**

In order to better protect the safety and interests of the subjects, the protocol of the trial is strictly followed and the quality of the trial data is ensured. The test site must be equipped with necessary medical rescue equipment, first-aid drugs and emergency measures. When necessary, an emergency medical emergency team shall be set up to deal with emergency medical events and accidental disasters in

accordance with relevant standard operating procedures. Closely observe possible adverse events, especially non-expected adverse events, timely analysis and communication, and record adverse events. Establish linkage procedures with the hospital intensive care unit for subject transfer and care. Establish communication and communication between researchers and laboratories and cooperative units to ensure timely communication and treatment of possible adverse events.

## **8.2 Infusion reaction**

Subjects will be monitored for signs and symptoms of infusion reactions (e. g., fever and / or chills, flushing and / or pruritus, changes in heart rate and blood pressure, dyspnea or chest discomfort, rash, etc.) and systemic allergic reactions (e. g., generalized urticaria, angioedema, asthma, hypotension, tachycardia).

In this study, to avoid confounding the potential safety signals regarding the assessment of the infusion response:

- 1) Primary prophylaxis is not allowed for infusion reactions (in subjects without infusion events).
- 2) The investigator may decide regarding appropriate secondary prevention (that is, preventing reactions related to infusion after the initial episode):

- An acetaminophen / paracetamol and / or antihistamine (e. g. diphenhydramine) may be administered approximately 30 minutes before the start of a subsequent infusion, and / or glucocorticoids or equivalent drugs according to the diagnostic routine at each center.
- Non-sedating antihistamines (e. g. cetirizine) may be considered for subjects with repeated infusion reactions.
- If the symptoms persist, the corticosterotherapy should be considered.
- According to the routine of each center, the investigator may at his discretion decide whether to administer piperidine / morphine sulfate and promethazine or the equivalent prior to the start of the subsequent infusion.

Readministration of pretreated agents may be required during the infusion; therefore, this should be considered in determining the dose of pretreated agents. Any

significant reactions and use requirements related to corticosteroids must be discussed with the medical monitor.

In the event of a level 2 infusion reaction, the infusion rate of AK 104 can be reduced by 50% or interrupt the infusion until the event resolves (up to 6 hours) and restart the infusion at 50% of the initial infusion rate after event resolution until the infusion is completed. Once the infusion rate of AK 104 is reduced by 50% or the infusion is interrupted due to the infusion reaction, all subsequent infusion must be continued at the reduced infusion rate. If the subject has a second level 2 infusion reaction at a slower infusion rate, the infusion should be stopped. If the subject has a grade 3 or 4 infusion reaction at any time, the AK 104 treatment must be stopped.

If severe hypersensitivity (grade CTCAE 3 or 4) is observed during the infusion, the infusion will be stopped immediately and no further AK 104 treatment will be given. Supportive treatment is provided according to the standard medical practice. If subjects develop symptoms or signs of systemic anaphylaxis or type 1 hypersensitivity during AK 104 administration, they will be treated with appropriate drugs and medical devices that will always be available at all sites. Glucocorticoids, epinephrine, allergic drugs (antihistamines) or equivalent should be readily available. The subject should be informed to report to the investigator on any delayed response.

Guidelines for toxicity management of AK 104 treatment related to infusion reactions are shown in the table below. In case of multiple low-grade AEs (permanent AK 104 treatment is not required separately), the permanent AK 104 treatment will be determined at the discretion of the investigator.

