**Table 1 Treatment adjustments for infusion response symptoms caused by AK**

104	
NCI-CTCAE grade	Regarding the treatment adjustment for AK 104
Level 1 mild Minor, temporary reaction; no infusion	Reduce the AK 104 infusion rate by 50% and closely monitor any deterioration. The total infusion time of AK 104 should not

interruption; no treatment.	exceed 120 minutes.

Level 2 moderate
 
Treatment or infusion interruption is required, but symptomatic treatment (such as antihistamines, NSAID, corticosteroids, intravenous infusion), rapid effect; preventive administration of <24 hours.
	
Interrupt the AK104 infusion.
 
The infusion was restarted at 50% of the previous infusion rate at times when the infusion response had subsided or the severity had dropped to at least level 1, and any deterioration was monitored closely.
 
If the subject has a second level 2 infusion reaction at a slower infusion rate, the infusion should be discontinued and the subject must be withdrawn from AK 104 treatment.

Grade 3 or 4 is serious or life-threatening
 
Grade 3: delay in symptom relief (e. g. symptomatic treatment and / or infusion interruption, lack of rapid response); relapse after symptom improvement; sequelae requiring hospitalization.
 
Grade 4: life-threatening; requiring urgent treatment.
	
The AK 104 infusion was stopped immediately, and the subject's infusion tube was disconnected.
 
Subjects must immediately withdraw from AK 104 treatment and must not receive any further AK 104 treatment.

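### Section 8.2 and its Table 1 give conflicting instructions for a grade 2 AK 104 infusion reaction, and nothing says which prevails

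*Protocol*

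**What the plan says.** Section 8.2 deals with infusion reactions twice, first in running text and then in Table 1, which a sentence between them introduces as the guidance for managing these reactions.

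For a grade 2 reaction the running text says that "the infusion rate of AK 104 can be reduced by 50% or interrupt the infusion until the event resolves (up to 6 hours"), and that after an interruption the site is to "restart the infusion at 50% of the initial infusion rate after event resolution until the infusion is completed". Once the rate has been halved or the infusion interrupted, "all subsequent infusion must be continued at the reduced infusion rate". On recurrence it says: "If the subject has a second level 2 infusion reaction at a slower infusion rate, the infusion should be stopped". The sentence after that ends AK 104 treatment for a grade 3 or 4 reaction.

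The grade 2 row of Table 1 begins "Interrupt the AK104 infusion" and offers no alternative. It continues: "The infusion was restarted at 50% of the previous infusion rate at times when the infusion response had subsided", or had fallen to at least level 1. For a second grade 2 reaction at the slower rate, "the infusion should be discontinued and the subject must be withdrawn from AK 104 treatment".

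The grade 1 row of Table 1 halves the rate and adds a limit, "The total infusion time of AK 104 should not", which the table sets at 120 minutes.

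**The concern.** Two sets of operative instructions cover the same event. A site that follows only the running text can act in a way that departs from Table 1, and both are protocol. The difference with most consequence is the second grade 2 reaction: under one rule the subject leaves AK 104, under the other the protocol states only that the infusion stops. That can change how long a subject is treated, and it feeds the summary of adverse events leading to discontinuation that the synopsis plans under safety. The restart-rate difference matters for a subject who reacts after the rate has already been halved. Under one reading of the text, that subject restarts at the same rate at which the grade 2 reaction occurred.

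**Working it through.** **Side by side, grade 2 reaction (section 8.2)**

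| Point | Running text | Table 1 |
|---|---|---|
| First action | Halve the rate, or interrupt | Interrupt |
| Restart condition | Event resolved; interruption up to 6 hours | Subsided, or at least down to level 1; no time limit |
| Restart rate | 50% of the *initial* rate | 50% of the *previous* rate |
| Second grade 2 at the slower rate | Stop the infusion | Stop the infusion and withdraw from AK 104 |

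**Is there a tie-break?** The sentence introducing Table 1 gives no precedence. The clause at the end of section 8.4 that sends inconsistencies to a meeting concerns immune-related events, and conflicts with other guidelines or local practice. It does not cover a conflict between two parts of section 8.2.

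**Restart rate.** Let the starting rate be R, and take *previous* as the rate running just before the interruption.

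- First reaction, at full rate. Text: 0.5 × R. Table: 0.5 × R. No difference.
- Grade 1 reaction has halved the rate earlier in the same infusion, then grade 2. Text: 0.5 × R. Table: 0.5 × 0.5R = 0.25R. A two-fold difference.
- Rate was halved at an earlier infusion and carried forward, then grade 2. If *initial* means the subject's starting rate, the text gives 0.5R and the table 0.25R. If *initial* means the rate at which this infusion began, the text gives 0.5 × 0.5R = 0.25R, the same as the table.

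So the rates conflict only after an earlier halving, and then depend on what *initial* means.

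**Second grade 2 reaction.** The text does not say that AK 104 continues. It does, however, speak of the infusion at grade 2 and of the treatment at grade 3 or 4, in adjacent sentences, and Table 1 lists stopping the infusion and withdrawal as two separate acts. The natural reading of the text therefore leaves later cycles open. The ceiling on what is at stake follows from section 3.1, which gives dosing on day 1 every 21 days for at most 24 months (taken as 730 days): floor(730/21) + 1 = 34 + 1 = 35 doses. If the second reaction falls at dose k, Table 1 removes up to 35 − k later doses. Most subjects would stop sooner for other reasons.

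**How many subjects?** The monotherapy table in section 1.1.2 shows treatment-related infusion reactions in 17 of 228, of which 6 were grade 3/4.

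- Below grade 3: 17 − 6 = 11, and 11/228 = 4.8%.
- Expected among 30: 30 × 11/228 = 1.45.
- The 6 with grade 3/4 may have had lower-grade reactions too. Counting all 17 gives 30 × 17/228 = 2.24.

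The rate and withdrawal conflicts need a repeat: grade 1 then grade 2, or two grade 2 reactions in one subject. The protocol gives no rate for either. If, as an assumption, 10% to 30% of the 1.45 had such a sequence, that is 0.15 to 0.43 subjects in 30.

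**The case against.** The best answer is that the table completes the text and a site can satisfy both. Interrupting is one of the text's two options; waiting for full resolution meets both restart conditions; stopping the infusion and withdrawing the subject meets both rules on recurrence. The text is silent on withdrawal rather than opposed to it, and the contrast between infusion and treatment rests on wording in a translated document. It stands that the text never says AK 104 continues, and that a first grade 2 reaction at full rate gives the same restart rate either way. This does not remove the conflict. A course that satisfies both exists, but neither passage directs the site to it, and a site relying on the text alone may slow without interrupting, or give a later cycle, and so depart from Table 1. Loose translation might explain *initial* against *previous*; it does not readily explain an option present in one place and absent in the other, or an added withdrawal.

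Four stronger readings are tempting and are not supported.

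- A reader might infer that the conflict acts on the primary safety endpoint through discontinuations. Section 2.2.1 defines that endpoint as adverse-event incidence and severity and significant laboratory abnormalities; discontinuation appears only among the safety summaries.
- A reader might compute 1 − (217/228)^30 = 0.77 and call it the chance that the conflict arises. That is the chance of at least one reaction below grade 3, from monotherapy data mainly at 6 mg/kg and 450 mg, not of the sequences that the rate and withdrawal conflicts need under this trial's regimen with chemotherapy.
- A reader might infer that every grade 2 reaction leads to different exposure. For a first reaction at full rate both rules allow the dose to be completed.
- A reader might see the 120-minute limit as contradicting the carried-forward half rate. If a full-rate infusion takes T minutes, a half-rate one takes 2T, so both hold when T is 60 or less. The protocol gives no T, and the limit stands only in the grade 1 row. It is an ambiguity, separate from the grade 2 conflict.

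**Conclusion.** The point holds as an internal inconsistency in a safety instruction. The text and Table 1 differ on the first action, the restart condition, the reference rate and the stated consequence of a second grade 2 reaction, with no precedence between them. The restart rates differ by a factor of two, but only after an earlier halving and only under some readings of *initial*. The recurrence rule is the weightiest item, because it bears on whether a subject stays on AK 104 and on the planned discontinuation summary.

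The numbers are small. On the protocol's own monotherapy figures, between one and two of 30 subjects would have a reaction below grade 3, and a repeat sequence would be rarer. This assumes that monotherapy rates carry over to this combination and schedule, which the protocol does not show. The case for correction rests on subject safety and on having one rule to follow, not on a large effect on the results.

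**What to change.** Amend section 8.2 so that one passage holds the rule for a grade 2 reaction, and replace the other with a cross-reference. The single rule should state:

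- one action at the first reaction;
- one restart condition, with or without a time limit;
- one reference rate, defined so that it is clear whether it means the subject's starting rate, the rate at the start of that infusion, or the rate just before the interruption;
- one consequence of a second grade 2 reaction, saying expressly whether it ends that infusion or all AK 104 treatment.

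Which rule stands is for the sponsor and medical monitor; this review takes no view. As a secondary clarification, say to which infusions the 120-minute limit in the grade 1 row applies. The cost is a short amendment and a notice to the site, with no additional subjects, staff or procedures.
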